### **Postoperatively:**

Following transfer to recovery unit, if patient reports pain score by numerical rating score >3, morphine 2 mg increments will be given intravenously by the recovery staff. This will be repeated every 5 minutes till the pain score is <4. In patients needing more than 10 mg of morphine in the recovery, anaesthetist will be requested to review the patient. Post-operatively, in the absence of contraindications, all patients will be prescribed regular paracetamol 1g every 6 hourly and celecoxib 200 mg, 12 hourly. Anti-emetics (ondansetron 4 mg, 8 hourly and Cyclizine 50 mg, 8 hourly) will be prescribed for all patients to be administered as required. All patients will receive morphine PCA in post-operative period. All patients will be reviewed at 6 hours and 24 hours to assess the pain scores and motor block.

Statistics:

A sample size of 46 patients (23 per group) is estimated based on 50% reduction in morphine consumption with power of 80% and alfa error of 0.05%. To allow for the drop outs, we aim to recruit 50 patients in total.

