## METHODS

This prospective, randomised controlled trial will be conducted in patients undergoing total hip replacement surgeries under spinal anaesthesia. Ethical committee approval has been obtained from the Research Ethics Committee (REC) in Tallaght hospital and the study will be registered in Clinicaltrials.gov database. All patients scheduled for elective total hip replacement surgery will be contacted up to 24 hours prior to the surgery by telephone. Information about the nature and purpose of the study will be provided to them by Anaesthetic trainees who are part of the study team. Informed written consent will be obtained from all consenting patients prior to participation in the study.

Randomisation will be carried out by computer generated random numbers and allocation will be enclosed in sealed envelopes. Patients and Outcome assessors will be blinded to the study group. The following are the inclusion and exclusion criteria.

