***Primary Outcome Measure:***

24 hour morphine consumption between the two groups

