***Transmuscular Quadratus Lumborum Block (TQL):***

Following the administration of spinal anaesthetic, the patient will be positioned laterally with the operating side as the non dependant side. Skin decontamination of the block site will be done with 2% Chlorhexidine (Chloraprep 3 ml applicator, CareFusion Corporation, San Diego, CA 92130, USA). Under strict aseptic precautions (cap, mask, sterile gloves, sterile probe cover

and sterile ultrasound gel), a 100 mm (Stimuplex® Ultra 360® 22 gauge insulated echogenic needle with 30° bevel and extension set) needle will be used to perform TQL block. A curvilinear low frequency probe (2-5 MHz) will be placed above the iliac crest and the following structures will be identified i) Transverse process ii) Erector spinae muscle iii) Quadratus lumborum muscle iv) Psoas major muscle. The needle will be advanced by in-plane technique and local anaesthetic will be deposited between psoas major and quadratus lumborum muscles. 20 ml of 0.25% bupivacaine will be administered under USG guidance following careful intermittent aspiration.

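### Recovery staff and the anaesthetist who reviews above 10 mg handle part of the primary morphine outcome, yet the protocol neither names them as blinded nor conceals the block from them

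*Protocol*

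**What the plan says.** The METHODS section of the protocol gives the whole blinding statement: "Patients and Outcome assessors will be blinded to the study group". It does not define outcome assessor and names no other role.

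The only primary outcome is "24 hour morphine consumption between the two groups". Neither the start of the 24 hours nor the sources of morphine to be summed are given.

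Under Postoperatively, morphine comes by two routes:

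- **Recovery unit.** The trigger is "if patient reports pain score by numerical rating score >3". Then "morphine 2 mg increments will be given intravenously by the recovery staff", and "This will be repeated every 5 minutes till the pain score is <4". Beyond a set amount there is a further step: "In patients needing more than 10 mg of morphine in the recovery, anaesthetist will be requested to review the patient". What that review may change, and who carries it out, is not stated.
- **Afterwards.** "All patients will receive morphine PCA in post-operative period".

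The two block sections describe different positions and sites. For the TQL block, "the patient will be positioned laterally with the operating side as the non dependant side", with the probe above the iliac crest. For the FIB the patient lies supine and the probe is at the groin. Volume and concentration are the same in both arms. No sham injection, common dressing, neutral chart entry or handover rule is described.

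**The concern.** The primary outcome is an amount of drug given, so the people who give it help to generate the data. In recovery, staff ask for the score, record it and act on it, and an anaesthetist may be drawn in above 10 mg. A trial that follows this protocol to the letter could have both roles filled by people who know the block, because nothing forbids it and nothing hides it.

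The Introduction states the expectation that TQL gives better analgesia. Staff who share or doubt that expectation might ask for scores more or less readily, re-ask more or less promptly at the 5-minute interval, or call for review at different points by arm. Blinding whoever scores pain and motor block at 6 and 24 hours does nothing for morphine already given in recovery. Masking also cannot be restored at the analysis stage, so this belongs in the protocol and not in an SAP.

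**Working it through.** **1. Who can influence what**

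| Step in the 24 h | Who acts | Fixed by rule? | Stated as blinded? |
|---|---|---|---|
| Reporting the score | Patient | Not applicable | Yes |
| Asking for and recording the score in recovery | Recovery staff (inferred) | Threshold and 5-minute repeat fixed; manner of asking not | Not named |
| Giving IV morphine | Recovery staff | Yes: start above 3, 2 mg steps, stop below 4 | Not named |
| Review above 10 mg | An anaesthetist | Trigger fixed; consequence not stated | Not named |
| PCA | Patient | Patient-controlled | Yes |
| Scores and motor block at 6 and 24 h | Reviewer not named | Times fixed | If counted as an outcome assessor |

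Two steps are therefore open to knowledge of the block: how scores are obtained and followed up in recovery, and what the review above 10 mg leads to. The anaesthetist who places the block necessarily knows the allocation, and nothing prevents that person from being the reviewer.

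**2. Is recovery morphine in the primary outcome?** The protocol does not say so outright. A 24-hour total that starts at or before arrival in recovery includes it; one that starts later does not.

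**3. How large could it be?** The protocol gives no control mean or SD, so there is no stated figure to reproduce. I assume a control total of 20-40 mg.

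- Increments before review is triggered: 10 mg / 2 mg = 5.
- One increment as a share of the control total: 2/40 = 5% to 2/20 = 10%.
- Planned 50% reduction: 0.5 × 20 = 10 mg to 0.5 × 40 = 20 mg.
- One increment more in every patient of one arm, as a share of that target: 2/20 = 10% to 2/10 = 20%.
- If it happened in only one patient in four of one arm, the mean shift would be 2 × 0.25 = 0.5 mg, or 0.5/20 = 2.5% to 0.5/10 = 5% of the target.

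**4. Effect on the type I error.** Assume a two-sided 5% test with exactly 80% power for the planned difference (the Statistics paragraph prints 0.05%; 5% is my assumption). The planned difference is then 1.960 + 0.842 = 2.802 standard errors. A bias of fraction f of it, with no true effect, gives a rejection probability of 1 − Φ(1.960 − 2.802f) + Φ(−1.960 − 2.802f).

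- f = 0.10: about 5.9%.
- f = 0.20: about 8.7%.

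**The case against.** The strongest reply is that the dosing rule is itself a safeguard. Trigger, increment, interval and stopping point are all fixed, and they depend on the score of a patient stated to be blinded. Staff who follow the rule have no freedom over the dose. This stands. A reader might infer from the word *given* that recovery staff decide the dose and that their knowledge enters the endpoint directly. The protocol does not support that; any influence must pass through how the score is obtained and followed up.

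Four further points also stand, in whole or part.

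- **Silence is not unblinding.** A reader might infer that recovery staff know the allocation. The protocol does not say so, and since outcome assessor is undefined, whoever records the score in recovery might be meant. That handover names the block, or that the reviewer is the one who placed it, would be an assumption about practice.
- **PCA follows.** All patients then control their own morphine, and a dose not given in recovery may be partly made up later. A 2 mg difference need not carry through to the 24-hour total.
- **The illustration is an upper one.** Only patients reporting a score above 3 receive any recovery morphine, and residual spinal block may keep that number low. Nothing in the protocol shows how many would exceed 10 mg.
- **Masking the chart alone would not suffice.** The injection sites differ visibly by arm, so the dressings must be dealt with too.

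What the reply does not remove is that the manner and timing of asking and the outcome of the review are not fixed, and that no concealment from these roles is described.

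**Conclusion.** The point holds in limited form. The protocol leaves two roles that handle staff-given morphine outside its blinding statement and describes no means of concealing the block from them. Bias can arise only indirectly, and only in the staff-given part of the 24-hour total. Its size is unknown.

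The figure of 10-20% of the planned reduction, with a type I error of about 5.9-8.7%, is an upper illustration. It rests on an assumed control total of 20-40 mg, a differential increment in every patient of one arm, no compensation through PCA, and a two-sided 5% test. It also presumes that recovery morphine is counted, which the wording suggests but does not state.

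The change is worth making because it is cheap, concerns the only primary outcome, and cannot be made after recruitment. It does not show that the result would be invalid without it.

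**What to change.** 1. **METHODS:** extend the blinding statement to recovery staff who score pain and give morphine and, where one is available, to a reviewing anaesthetist who did not place the block.
2. **Block sections and Postoperatively:** have the anaesthetic chart and the handover record *study block, 20 ml 0.25% bupivacaine*, which is true in both arms, with the allocation in a sealed envelope in the notes for emergencies.
3. **Block sections:** cover both possible block sites with identical dressings in every patient.
4. **Primary Outcome Measure:** state that the outcome is recovery IV morphine plus PCA morphine, counted over 24 hours from a fixed start time no later than arrival in recovery.

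The cost is a charting and handover convention and one extra dressing per patient, with no extra staff. The downside is that staff must open the envelope if a complication requires the block site to be known; each opening should be logged. No dose, trigger or other clinical rule changes.

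### The only type I error rate in the protocol is printed as 0.05% (0.0005), almost certainly a slip for 0.05 (5%); the sponsor should confirm the level used and correct the text

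*Protocol*

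**What the plan says.** The primary outcome is "24 hour morphine consumption between the two groups" (Protocol, Primary Outcome Measure). The sample size is given in the Statistics paragraph that closes the Postoperatively section: "A sample size of 46 patients (23 per group) is estimated based on 50% reduction in morphine consumption". The same sentence then states the error rates that were used: "with power of 80% and alfa error of 0.05". In the protocol a percent sign follows that last figure, so the printed type I error is 0.05%, or 0.0005 as a proportion. The paragraph then adds an allowance for losses: "To allow for the drop outs, we aim to recruit 50 patients in total".

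The calculation therefore has three stated inputs: the relative reduction, the power and alpha. The protocol gives no control-group mean, SD, test or sidedness, and no other alpha, significance level or confidence level.

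**The concern.** A type I error of 0.0005 is 100 times stricter than 5% (0.05 / 0.0005 = 100). A protocol that meant it would normally give a reason, such as many comparisons or interim looks. This one has two arms and one primary outcome, and describes neither interim analyses nor a multiplicity adjustment. The likely explanation is that 0.05 was meant and a percent sign was added, perhaps carried over from the 80% in the same sentence.

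Two things are at stake:

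- **Basis of the sample size.** The two readings imply quite different variability in morphine use, so the printed text does not establish what the 46 patients rest on.
- **Threshold for the primary comparison.** This is the only level the protocol states. If it were carried into the analysis, p-values between 0.0005 and 0.05 would not count as significant. If the trial reports at 5% instead, it departs from the only level in its protocol.

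**Working it through.** **Inputs from the protocol (Statistics paragraph).** 23 per group, power 80%, relative reduction 50%, alpha printed as 0.05%.

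**Assumptions, because the protocol gives none.** Comparison of two means, equal SDs, 1:1 allocation. The main case is a two-sided t-test; one-sided tests and the normal approximation give the range.

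**Step 1: can the 46 be reproduced?** Not outright, since there is no mean or SD. What can be done is to solve for the standardised difference d that 23 per group detects with 80% power, and convert it to an SD. The difference is half the fascia iliaca block (FIB) mean, so SD / FIB mean = 0.5 / d.

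Normal approximation: d = √(2/23) × (z for alpha + z for power), with √(2/23) = 0.295 and z for 80% power = 0.842.

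- Two-sided 0.05: d = 0.295 × (1.960 + 0.842) = 0.826, so SD / mean = 0.5 / 0.826 = 0.605.
- Two-sided 0.0005: d = 0.295 × (3.481 + 0.842) = 1.275, so SD / mean = 0.5 / 1.275 = 0.392.

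All four methods, with the t rows from the noncentral t distribution on 44 degrees of freedom:

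| Method | d at 0.05 | SD / mean | d at 0.0005 | SD / mean |
|---|---|---|---|---|
| t, two-sided | 0.845 | 0.592 | 1.369 | 0.365 |
| t, one-sided | 0.745 | 0.671 | 1.299 | 0.385 |
| Normal, two-sided | 0.826 | 0.605 | 1.275 | 0.392 |
| Normal, one-sided | 0.733 | 0.682 | 1.219 | 0.410 |

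So 23 per group fits an alpha of 5% if the SD is 59% to 68% of the FIB mean, and an alpha of 0.05% if it is 37% to 41%. The arithmetic alone rules out neither.

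**Step 2: does a round input point one way?** Required n per group, normal approximation, two-sided, is 2 × (SD/mean)² × (z sum)² / 0.5²:

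| Assumed SD / FIB mean | n at 0.05 | n at 0.0005 |
|---|---|---|
| 0.4 | 11 | 24 |
| 0.5 | 16 | 38 |
| 0.6 | 23 | 54 |
| 0.8 | 41 | 96 |
| 1.0 | 63 | 150 |

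An SD of 0.6 of the mean at 5% gives 2 × 0.36 × 2.802² / 0.25 = 22.6, rounded up to 23, which is the planned number. At 0.0005 the nearest round value, 0.4, gives 24. This supports the slip reading but does not prove it.

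**Step 3: dropout allowance.** 46 / 50 = 0.92, so 8% losses are allowed for. That step is consistent and does not depend on alpha.

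**Step 4: what mixing the two levels would do (illustration only).** Suppose the trial was sized at 5% and 0.05% was then applied, each method keeping its own d from Step 1.

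| Method | Power at 0.0005 with 23 per group | n per group for 80% |
|---|---|---|
| t, two-sided | 20.9% | 56 |
| t, one-sided | 17.9% | 65 |
| Normal, two-sided | 24.9% | 55 |
| Normal, one-sided | 21.1% | 64 |

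In the reverse case, if 0.05% really was used, d = 1.369 (two-sided t) would need only about 10 per group at 5%.

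**The case against.** The strongest reply is that this is a notation slip most readers correct at sight. If 5% was meant, no patient, target or endpoint changes. Alpha is stated as an input to the sample size, not as a decision rule. The analysis threshold may sit in a statistical analysis plan that is not shown, and nothing in the protocol says the morphine comparison will be judged at 0.0005. The power and sample-size figures for mixed levels describe a situation that no section of the protocol sets out.

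Much of this stands. The 21% power figure is not a claim that the trial is underpowered. The 46 patients are not shown to contradict 0.0005. Correcting alpha alone would not make the 46 checkable, because the mean and SD would still be unstated. Which alpha was used is a matter of judgement; the arithmetic does not prove it.

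The error itself is not answered, however. The figure concerns the primary comparison, it is the only error rate in the document, and nothing elsewhere in the protocol corrects it. An analysis plan could state the right level, but the protocol would then disagree with it.

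**Conclusion.** The concern holds: the printed alpha is almost certainly wrong, by a factor of 100. That judgement rests on convention, on the absence of any reason in the design for so strict a level, and on the exact match to 23 per group at 5% with an SD of 0.6 of the mean.

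The two readings imply an SD of about 59% of the FIB mean (range 59% to 68%) or about 37% (range 37% to 41%), so the basis of the 46 is ambiguous as printed. These figures depend on a comparison of two means with equal SDs. If 5% is confirmed, the consequence is confined to the text. If 0.05% was truly intended, the protocol should say why. The point deserves correction because of where the figure stands, but it does not show a fault in the size of the trial.

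**What to change.** The sponsor should go back to the original calculation, confirm the alpha used, and correct the Statistics paragraph, presumably to an alpha of 0.05 (5%), adding that it is two-sided if so. The same level should be applied to the 24-hour morphine comparison. Stating the assumed mean and SD in the same sentence would also let a reader check the 46.

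If 5% is confirmed, the 46 patients and the target of 50 stay as they are. The cost is one wording correction, with no added patients, visits or staff.
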